10.1.2 Baseline Values for Patient Reported Outcome Assessments

For the Patient Reported Outcome (PRO) assessments PROMIS-short form-Fatigue 7b Daily, PGIS Fatigue and Pruritus and WI-NRS introduced in protocol version 2.0, subjects enrolled under protocol version 1.0 will not have a baseline value collected. The baseline value for subjects enrolled under version 1.0 for these questionnaires will be imputed prior to analysis (Section 12.5.3). For the PBC-40, only the recall period was changed and the baseline value captured under protocol version 1.0 is considered relevant.

10.1.3 Baseline Values for Other Endpoints

For all other efficacy and safety endpoints, baseline is defined as the last non-missing assessment obtained prior to the first administration of study drug. Where time of assessment is not collected and the assessment is collected on the same date as the first dose of IMP, the assessment will be assumed to be per protocol i.e. prior to first dose administration. If multiple continuous assessments for safety and efficacy endpoints occur on the same day as first dose and no time is recorded, the arithmetic mean will be used as baseline. If multiple categorical assessments occur on the same day as first dose and no time is recorded, the worst severity will be used as the baseline value.

10.1.4 Baseline Values for Extension Phase

For subjects enrolled into the Extension Phase under protocol versions 1.0 to 4.0, "Extension Baseline" value will be defined as the value obtained prior to receiving the first dose of the active treatment. Thus, for subjects who were initially randomized to receive placebo and then switched to setanaxib in the extension phase, the value obtained prior to receiving the first administration of active drug will be the extension baseline value.

10.1.5 Change from Baseline

If the value at baseline and at post-baseline timepoint are not missing, change from baseline at any post-baseline time point will be defined as:

Change from baseline = value at post baseline time point - value at baseline

Percentage change from baseline at any post-baseline time point will be defined as:

Sponsor: Calliditas Therapeutics Suisse SA

Protocol No: GSN000350

Percentage change from baseline =
$$100 * \frac{(value \text{ at post baseline time point} - value \text{ at baseline})}{Value \text{ at baseline}}$$

Fold change from baseline at any post-baseline time point will be defined as the below ratio:

Fold change from baseline =
$$\frac{value \text{ at post baseline time point}}{value \text{ at baseline}}$$

For the primary endpoints, reductions in ALP from baseline will be defined as:

Reductions in ALP from baseline =
$$100 * \frac{(value \ at \ baseline - value \ at \ post \ baseline \ time \ point)}{value \ at \ baseline}$$

10.2 Study Day

Study Day 1 is defined as the first date of study treatment.

• For dates prior to Study Day 1, the Study Day is calculated as:

• For dates on or post Study Day 1,

If the patient was never treated, the date of randomization will be used in lieu of the first date of study treatment in the above calculations.

For subjects enrolled into the Extension Phase under protocol versions 1.0 to 4.0, study day in the Extension Phase may be defined from the date of first dose of setanaxib in the extension phase.

10.3 Visit Windowing

Subjects may not be able to attend visits on protocol specified days. For the purposes of the analysis, observations will be assigned to analysis windows (Tables 1a and 1b). Table 2 displays the analysis windows to be applied for any subjects enrolled under protocol versions 1.0 to 4.0 and entered in the extension phase.

Tabulations will summarize scheduled time points only. All visits (including unscheduled and EoT visits) will be windowed to the appropriate analysis visit regardless of the visit label entered in the eCRF.

For the efficacy data (including a selection of the liver functions tests, liver stiffness as assessed by fibroscan and QoL),

- If more than one measurement falls within a visit window, the geometric mean (for ALP, ALT, AST, total and direct bilirubin, GGT and liver stiffness) and arithmetic mean (for QoL) of all measurements within the window will be used in the analysis.
- For the same endpoints described above, if data for the week 24 assessment is missing, but an EOT result at week 28 is available, the week 24 result will be substituted by the week 28 result. The week 28 result will also be retained in summary tables.
- For a small number of patients (<5) who had liver stiffness values captured at week 8 without a further assessment at week 12, the week 8 result will be carried forward to week 12 in the analysis. The week 8 result will also be retained in summary tables.
- For QoL assessment collected using a daily diary over multiple days prior to the visits (including WI-NRS and PROMIS-Short Form-Fatigue 7b Daily), the last assessment within the window will be used to define the analysis visit for each assessment. When deriving the baseline, the 7 days prior to the start of treatment will be included. If the questionnaire was incorrectly completed over 8 or more days, the additional records will not be included in the calculation of baseline. For post-

Sponsor: Calliditas Therapeutics Suisse SA

Protocol No: GSN000350

baseline assessments, if there are 8 recorded collected, they will be included in the calculation of arithmetic means.

For all other assessments (including all other liver function tests captured in Table 8 [serum fibrinogen, albumin, hsCRP and IgM]), the value closest to the target day will be selected for use in the analysis. If more than one assessment is equidistant from the target day, the assessment later in time will be selected. If there is more than 1 record on the selected day, the arithmetic mean of the continuous assessments will be applied, or the worst assessment (for categorical parameters) will be selected. If there is an EoT assessment and a scheduled assessment within a time point, the scheduled assessment should always be selected for use in the analysis. For analysis for determination of worst case values, for example shift tables to the worst post-baseline value, all post-baseline values collected during the time period defined by the analysis set, including unscheduled visits, will be considered.

Table 1a: Analysis Windows for Main Part

Analysis Visit	Target Study Day	Lower Limit	Upper Limit
Baseline	1		1 (pre-dose)
Day 1	1 (post-dose)		
Week 2	15	2	22
Week 4	29	23	43
Week 8	57	44	71
Week 12	85	72	127
Week 24	169	128	183
Week 28 - EOT	196	184	225

Table 2b: Analysis Windows for Main Part for ADQS domains (PROMIS-Short Form Fatigue 7b Daily, PBC-40, PROMIS-29, EQ5L, PGIC, PGIS and WI-NRS)

Analysis Visit	Target Study Day	Lower Limit	Upper Limit
Baseline	1		1 (pre-dose)
Day 1	1 (post-dose)		
Week 4	29	2	71
Week 12	85	72	127
Week 24	169	128	183
Week 28 - EOT	196	184	225

Table 3: Analysis Windows for data collected under protocol versions 1.0 to 4.0, including Extension Phase (EP)

Analysis Visit	Target EP Study Day	Lower Limit	Upper Limit
Week 36	253	226	309
Week 52	365	310	460

Sponsor: Calliditas Therapeutics Suisse SA

Protocol No: GSN000350

Extension Baseline	1		1 (pre-dose in Extension)*
Week 68/Week 16 Extension	113	2	155
Week 80/Week 28 Extension	197	156	239
Week 92/Week 40 Extension	281	240	323
Week 104/Week 52 Extension	365	324	407

^{*}for subjects on Placebo in the Main Part. Study day is relative to first dose in the Extension Phase.

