# SCHEDULE OF ASSESSMENTS

## Table 1Schedule of Assessments

Study Period	Scre	ening a	ĺ		Follow-up b,c,d					
Study Weeks:	-4 to -1		BL	2	4	8	12	16, 20	24	28
Study Days (Visit Window):	-28	to -4	1	15 (±3)	29 (±3)	57 (±7)	85 (±7)	113, 141 (±3)	169 (±14)	last IMP dose+30 (+7)
Visit:	1ª	2 a	3	4	5	6	7	Phone e	8	ЕоТ
Informed consent	Х									
Determination of eligibility f	Х	Х	$\mathbf{X}^{\mathrm{f}}$							
Randomization			Х							
Demographics and relevant medical history	Х		Х							
Height and body temperature	Х									
Body weight	Х								Х	Х
Physical examination g	Х	Х	Х	Х	Х	Х	Х		Х	Х
Pulse rate, SBP, and DBP	Х	Х	Х	Х	Х	Х	Х		Х	Х
12-lead ECG	Х		Х	Х	Х	Х	Х		Х	Х
Liver stiffness using transient elastography h	Х	Х					Х		Х	Х
Blood sampling:										
Liver biochemistry i	Х	$X^i$	Х	Х	Х	Х	Х		Х	Х
ELF score, PRO-C3, and C3M			Х						Х	Х
hsCRP, IgM			Х	Х			Х		Х	Х
Total bile acids, C4, FGF19, FGF21			Х						Х	Х
Autoantibodies, j viral serology k	Х									
Pregnancy test (serum) 	$\mathbf{X}^{l}$	$X^l$								
Hematology and biochemistry m	Х	Xi	Х	Х	Х	Х	Х		Х	Х
TSH and free T4	Х	$\mathbf{X}^{\mathrm{i}}$	Х	Х	Х	Х			Х	
PK (morning predose)					Х				Х	
Biomarker (optional)			Х						Х	
Optional collection of DNA sample			Х							
Urine collection:										
Urine drug screen	Х									
Urinalysis n	Х						Х		Х	Х
Pregnancy test (urine)			Х	Х	Х	Х	Х		Х	Х

Confidential

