a All patients will attend Screening Visit 1. If liver stiffness (see Footnote h) and/or liver biochemistry (see Footnote i) and/or serum pregnancy (see Footnote l) retests are required, patients will attend Screening Visit 2. Screening Visit 1 and, if required, Screening Visit 2 should be completed within 4 weeks prior to Randomization. If required, Screening Visit 2 should be conducted by Day -4. Screening Period extensions of up to 7 days may be considered on a case-by-case basis, if agreed by the Investigator and Medical Monitor.

b Patients who permanently discontinue IMP prior to completion of the 24-week Double-blind Treatment Period will have an EoT Visit 30 days after the last IMP dose, after which every possible effort should be made to complete the Week 24 Visit (Visit 8).

c Patients who complete the 24-week Double-blind Treatment Period will have an EoT Visit at 30 days after the last IMP dose.

d The EoT Visit will be the EoS Visit for a) patients who withdraw from the study before the Week 24 Visit (Visit 8), and b) patients who are following the previous protocol schedule and are already beyond Week 24.

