9.6.4 Per Protocol Analysis Set

Per Protocol analysis set (PPS) comprises of all subjects in the FAS who do not have any important protocol deviations during the 24-week treatment period that would potentially affect the efficacy of the study drug. Subjects will be analyzed based on the treatment group they were randomized to regardless of the actual treatment received.

Important protocol deviations are defined in the Protocol Deviation Guidance Document for the study. Prior to database lock and unblinding of the study, a blinded data review of the important protocol deviations (including programmatically determined deviations) will be performed to identify the important deviations impacting on the efficacy endpoints. This analysis set will be defined in a blinded manner prior to unblinding the study and agreed with Sponsor.

Deviations impacting efficacy that may lead to exclusion from the PPS will include:

- Deviations related to inclusion/exclusion criteria
- Incorrect treatment received (i.e. the actual treatment received is different to the initially randomized treatment at any point during the first 24-weeks of treatment)
- Non-compliance with study drug intake (≤80%) during the first 24-weeks of treatment
- Efficacy assessments at Week 24 performed significantly out of the protocol specified window
- Missing baseline data for the primary endpoint
- Use of prohibited concomitant medication that could have impacted the efficacy of study treatment.

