12.1 Subject Disposition

A summary of subject disposition will be provided by treatment group and total for the ENRL set. The number and percentage of subjects in the below categories will be summarized:

Analysis	Comment	
Subjects screened (total n only)		
Subjects randomized		
Subjects randomized but not treated		
Subjects treated		
Subjects who completed at least 24-weeks treatment	The subject will be defined as completing treatment if they complete the Week 24 exposure CRF visit (or Week 28 in the absence of Week 24).	
Subjects who discontinued treatment prior to 24-weeks with reasons for discontinuation		
Subjects who discontinued study prior to 24 weeks with reasons for discontinuation	A subject will be defined as completing the Study, if they complete Week 24 CRF visit.	
Subjects who completed at least 52-weeks treatment (protocol version 1.0 to 4.0)	The subject will be defined as completing treatment at least 52-weeks if they complete the Week 52 exposure CRF visit.	
Subjects who discontinued treatment prior to 52-weeks with reasons for discontinuation		
Subjects who discontinued the study prior to 52 weeks with reasons for discontinuation	The subject will be defined as discontinued study prior to 52-weeks if they do not complete the Week 52 exposure CRF visit.	
Subjects enrolled in the extension phase	CRF Study Drug Administration (Extension Phase)	
 Subjects assigned to 1200mg 		
 Subjects assigned to 1600mg 		
Subjects treated in the extension phase	CRF Study Drug Administration (Extension Phase)	
 Subjects treated with 1200mg 		
o Subjects treated with 1600mg		

The flow of subjects through each stage of a trial, from recruitment to analysis, will be summarized using CONSORT (Consolidated Standards of Reporting Trials) diagram.

Screen failure and reasons for screen failure will be listed and summarized using the ENRL set.

Subjects disposition and screening information will be listed. For subjects who entered the extension phase, listings will include the dose received in the randomized phase and dose received in the extension phase together with dates.

Version Date: 27-June-2024

Sponsor: Calliditas Therapeutics Suisse SA

Protocol No: GSN000350

Enrollment will be summarized by region (North America, South and Central America, Europe, Asia, Africa), country and site by number enrolled, n(%) randomized and n(%) treated for the ENRL set.

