12.4 Important Protocol Deviations

Per ICON processes, protocol deviations data will be entered into the ICON system of record (PSO), in accordance with the Protocol Deviation Guidance Document. Important protocol deviations are defined in the protocol deviation guidance document. The final approved version of protocol deviation guidance will be finalized before the database lock for the primary analysis. The study team and the Sponsor will conduct on-going reviews of the deviation data from PSO, adjusting the deviation criteria as seems appropriate.

Protocol deviation data will be reviewed prior to database lock and important deviations with a potential impact on efficacy leading to the elimination of subjects from the PP will be identified. The PP must be finalized at the blinded data review meeting (or earlier), prior to database lock for the primary analysis and agreed with the Sponsor.

During the blinded data review meeting that was conducted prior to database lock, it was identified that several important deviations with impact on efficacy per section 9.6.4 were not entered into PSO. As such, programmatic PDs for deviations related to inclusion/exclusion criteria and non-compliance with study drug intake (≤80%) were derived and agreed in the blinded data review meeting and subsequently used as an additional protocol deviation source for analysis.

The number of subjects with important protocol deviations will be summarized in the FAS by category of violation and by treatment group including subset of Important protocol deviations leading to exclusion from the PP. For the primary analysis, all protocol deviations will also be listed. Deviations that occurred over a 24-weeks treatment period, over a 52-weeks treatment period and occurred during the extension phase will be flagged in the listings.

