12.5.2 Primary Estimand

For the primary efficacy analysis, each setanaxib treatment group (1600 mg and 1200 mg) will be compared with placebo. The primary estimand is to assess the change in ALP (%) over 24 weeks in subjects with PBC, elevated liver stiffness, and intolerance or inadequate response to UDCA.

The intercurrent events of Important protocol deviations impacting efficacy and treatment discontinuation prior to Week 24 for any reason not considered under the Composite Strategy (below) will be handled with a treatment policy strategy (the primary estimand) and the value recorded for the variable of interest is used regardless of whether or not the intercurrent event occurs (ICH E9 R1 addendum). The intercurrent events of starting additional PBC-related medications after randomization and prior to Week 24 or death prior to week 24 will be handled with a composite variable strategy, where efficacy data collected following the intercurrent event will be excluded from the primary analysis. PBC-related medication(s) will be identified through blinded medical review prior to database lock.

Table 6: Definition of Intercurrent Events

Intercurrent Event	Strategy	Comment
Important protocol deviations that impact efficacy	Treatment policy strategy	The occurrence of the intercurrent event is considered irrelevant in defining the treatment effect of interest, the value for the variable of interest is used regardless of whether or not the intercurrent event occurs
Starting additional PBC-related medications after randomization and before Week 24 Death before Week 24	Composite variable strategies	Efficacy data collected after these events will be excluded from the primary analysis.

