12.5.2.3 Supplementary Analyses

If there are important protocol deviations that impact efficacy, the primary analysis (see Section 12.5.2.1) will be repeated using the PPS. Subjects with important protocol deviations could falsely draw the estimated treatment difference closer. Exclusion of these subjects in this sensitivity analysis will help assess the magnitude, if any, of this effect.

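### SAP 10.3 fills a missing Week 24 ALP with the Week 28 EoT value; in version 5.0 treatment completers that is an off-drug reading in the primary analysis

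*SAP*

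**What the plan says.** SAP 10.3 (Visit Windowing) names ALP among the efficacy measures. For those measures, when Week 24 is missing but a Week 28 EoT result exists, "the week 24 result will be substituted by the week 28 result". SAP 12.5.2.1 fits the primary MMRM to ALP at Weeks 2, 4, 8, 12 and 24. It does not repeat the substitution, but 10.3 defines the analysis visits, so a substituted value enters the model as Week 24.

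Protocol Table 1 places the EoT visit in the Follow-up column, timed at "last IMP dose+30 (+7") days, with liver biochemistry (which includes ALP) drawn there. Footnote c reads: "Patients who complete the 24-week Double-blind Treatment Period will have an EoT Visit at 30 days after the last IMP dose". SAP 10.7.1 gives the same timing for version 5.0 completers.

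On the estimand, SAP 12.5.2 says that "treatment discontinuation prior to Week 24 for any reason not considered under the Composite Strategy (below) will be handled with a treatment policy strategy". Protocol 8.1 bases the primary analysis on data from the 24-week double-blind period. SAP 12.5.2.2 says the MMRM works on observed data and needs no separate imputation step.

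**The concern.** A completer's Week 28 sample is not a late Week 24 sample. By design it is taken about a month after treatment has ended. Treating it as the Week 24 response mixes on-drug and off-drug readings in the visit that carries the primary comparison. The estimand gives no reason for doing so: stopping at the planned end of treatment is not an intercurrent event before Week 24.

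If part of any ALP effect is lost off drug, each substituted setanaxib value pulls the Week 24 contrast toward no difference. With about 16 evaluable patients per arm, a few such values could matter, and the planned outputs would not isolate their influence.

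**Working it through.** **1. Timing.** Inputs: EoT at last dose + 30 days, window +7 (Protocol Table 1); Week 24 visit on Day 169 ±14 (Table 1); Week 28 analysis window Days 184 to 225 (SAP Table 1a). Assumption: a completer's last dose falls within the Week 24 visit window, Days 155 to 183.
- Earliest EoT: 155 + 30 = Day 185.
- Latest EoT: 183 + 37 = Day 220.
- Both lie inside Days 184 to 225, so the sample is windowed to Week 28 and is available for substitution.

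**2. Off drug or not.** Protocol 1.1.4 gives an elimination half-life of about 8 to 14 h. Thirty days is 720 h, and 720/14 = 51 and 720/8 = 90 half-lives. Drug exposure has ended by then. This says nothing about how fast ALP itself returns.

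**3. Who is affected.** The patient must be under version 5.0, have completed treatment, have attended EoT, and have no ALP of any kind in the Week 24 window of Days 128 to 183 (183 − 128 + 1 = 56 days). SAP 10.3 windows every visit by date, including unscheduled ones, so any sample in those 56 days fills the slot. Two groups are outside the concern: patients who stopped before Week 24, whose off-drug values fit the treatment policy strategy, and patients from versions 1.0 to 4.0 who may still be on drug at Days 184 to 225 (SAP 10.7.1).

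**4. Do other planned analyses remove the value?**
- Sensitivity Analysis #1 runs only if there is a significant amount of missing data and enough retrieved dropouts. A substituted slot is not missing, so the value stays. The WDAW5 covariate would code the completer as 0, meaning still on therapy.
- Sensitivity Analysis #2 depends on the residual plots. It too imputes only what is missing, so it keeps the value.
- The PPS repeat is also conditional: "If there are important protocol deviations that impact efficacy, the primary analysis" is repeated. One listed ground is "Efficacy assessments at Week 24 performed significantly out of the protocol specified window", but SAP 9.6.4 says only that such deviations may lead to exclusion and does not say whether the criterion applies to substituted values. SAP 12.4 adds "programmatic PDs for deviations related to inclusion/exclusion criteria and non-compliance with study drug intake", which does not include visit timing. Exclusion would also drop the whole patient rather than the one value.
- Week 28 results stay in the summary tables, so off-drug ALP is visible there, but its effect on the Week 24 contrast is not shown.

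**5. Illustration of size.** Inputs from SAP 8.1: reductions of 25% and 2.5%, and 16 evaluable per arm. Assumptions: these percentages are read as geometric ratios; k of the 16 values in a setanaxib arm are substituted; a fraction r of the log-scale effect is lost; placebo is unchanged; the Week 24 mean is a simple average.
- Planned: d = ln(0.75/0.975) = −0.262, and exp(d) − 1 = −23.1%.
- With substitution: exp[d(1 − rk/16)] − 1.

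| k | r = 1 (full loss) | r = 0.5 (half loss) |
|---|---|---|
| 1 | −21.8% | −22.4% |
| 2 | −20.5% | −21.8% |
| 3 | −19.2% | −21.2% |

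With r = 0 there is no change. Neither k nor r can be taken from the documents.

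**The case against.** The strongest objection is that the protocol leaves this to the SAP. Protocol 8.4.1.1 says missing results will be imputed from observed data with details in the SAP, and 8.4.5 says the same of missing ALP. A rule that fills Week 24 from an observed value falls within that delegation. This stands. A reader might infer from the rule's absence in SAP 6.1 that it is an undeclared change from protocol; the documents do not support that reading.

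The rule also has a sound use. Windowing ignores visit labels, so a Week 24 visit held on Day 184 or later falls in the Week 28 slot, and the substitution recovers it. This stands too, and any fix must keep such values.

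A reader might take SAP 12.1 as proof that completers without a Week 24 ALP exist, since it counts patients as completing treatment if "they complete the Week 24 exposure CRF visit (or Week 28 in the absence of Week 24"). That passage concerns the exposure form, does not mention ALP and is not limited to version 5.0. It shows no such patient. Given the 56-day window, the number is probably small.

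Finally, the bias would run against setanaxib, the trial is an exploratory Phase 2b, and listings and individual ALP plots would let a reader trace substituted values. That limits the seriousness. It does not make an off-drug reading a Week 24 response, and leaving the slot missing has its own cost: reliance on earlier visits under missing at random.

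**Conclusion.** The concern holds for one defined group: version 5.0 treatment completers with no ALP in Days 128 to 183 and a scheduled EoT sample. For them the plan analyses a reading taken 30 to 37 days after the last dose as the primary Week 24 response. The estimand gives no basis for this, and no planned analysis is certain to show its effect. The rule is within the SAP's remit but is not suited to completers.

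The direction is toward no effect if the ALP effect is lost off drug; if it is not lost, there is no bias. In the illustration the shift is at most 3.9 percentage points (23.1 − 19.2) with three of 16 values and full loss, and 1.9 points (23.1 − 21.2) with half loss. These figures rest on assumed counts and an assumed loss.

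A reader might also infer a definite loss of power, or a threshold of lost effect below which substitution is harmless. Neither can be stated. Both depend on whether the affected values lie in the setanaxib arms only, whether they are among the 16 or additional to them, and how much the MMRM recovers from earlier visits. The documents settle none of these.

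**What to change.** Amend SAP 10.3 for the primary MMRM: leave Week 24 missing for a treatment completer whose only value in the Week 28 window is the scheduled post-treatment EoT sample, taken about 30 days or more after the last dose. Keep three kinds of value: those from patients still on IMP, late Week 24 visits taken at or within a few days of the last dose, and those from early discontinuers under the treatment policy strategy.

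Run the present substitution rule as a sensitivity analysis, and report the number of substituted values per arm, split by on or off drug.

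The cost is a short change of SAP wording, one derivation flag based on days since last dose, and one extra model run. The downside is that a few more Week 24 values are left to the MMRM under missing at random.
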